Participants will be allowed as much time as needed, with Site Study personnel or in private, to review the HIPPA waiver and consenting documents before making the decision to participate. Potential participants may invite a friend or family member to be present during the visit, to further discuss their decision to enroll and/or contact (e.g., phone call) a friend or family member that is not physically present for discussion before deciding to enroll. At the potential participant’s request, Site Study personnel may be asked to ‘step-out’ of the room or end/mute the call during remote discussions, to provide privacy for such discussions. In addition, potential participants will be provided the option to defer their decision to allow them to review the consent form and other study information forms at their convenience, and later reconnect with the Site Study team remotely or return to the Study Site to enroll (i.e., complete the informed consent procedures). No study activities will take place prior to completion of the consenting process.

Participants will not be invited for consent discussions during periods of greater impairment. Participants must have been in outpatient status and on stable medications for 4 weeks prior to signing assent/consent. If a participant is hospitalized for psychiatric reasons during the study, they will be withdrawn from study activities. Additionally, consent to continue in the study will be addressed as needed throughout the study and the participant will be reminded that their participation in this study is completely voluntary and they do not have to continue unless they choose to.

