sessions per week and the weekly cognitive assessments. Participants will be informed that the study will work if the participant is unable to commit to recommended minimum EMA sessions per week and weekly cognitive assessments. The Site Study Coordinator may offer their support to work with the participant on a schedule that is feasible, given participant's current life circumstances, as appropriate. To ensure a time-bounded study commitment, after 12 weeks such participants will perform their post-intervention assessment (*End of Study, V3*) visit, given that they have met the minimum number of sessions required to complete this visit.

- *Extra Time:* : Under special circumstances, dCBGT session(s) may be paused for 1 or more weeks. This may occur if the WASABI Clinician is unable to conduct the session and no alternate WASABI Clinician is available to conduct the session. In such cases, the intervention will be extended by the number of weeks it has been placed on hold. Participants will resume the assigned dCBGT session such that all 12 sessions intended for the 12-week intervention are delivered to participants. Similarly, participant access to BrainHQ app will be extended by the same number of weeks. While the intervention is on hold, access to BrainHQ may be revoked and participants will not be asked to completed BrainHQ study activities until dCBGT sessions resume. Access to other study applications, such as Google Apps, Google Meet and Chat, may be available until the final dCBGT session is completed, but participants will not need to engage with these activities while the intervention is on hold and participants will be informed the WASABI Clinician will not be monitoring or engaging in the group chat.
- *Cessation of Program Use While Continuing Participation in the Study:* In some cases, a participant may wish to stop or minimize use of the program, while remaining in the study. Potential reasons for this decision might include changes in school or work circumstances, changes in residence, health issues, family/personal issues, or a lack of interest in program activities. While the participant will be encouraged to meet their weekly goals, in such cases, after discussion with the Site Study Coordinator, the participant will be permitted to cease using the program and undergo the post-intervention assessment (*End of Study, V3*) visit, given they have met the minimum number of sessions required to complete this assessment.

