Study participants may withdraw from the study at any time, for any reason, or for no stated reason. We anticipate that a common reason for study withdrawal will be the time required to complete the intervention. For participants seeking to withdraw for that reason, we will offer the alternative of discontinuing the intervention and scheduling and completing the post-intervention assessment (*End of Study, V3*) visit, given they have met the minimum sessions required to complete the post-assessment visits. The data analysis plan is structured so that their data will be valuable even if they do not complete the intended number of sessions. Participants who still wish to withdraw following that option will withdraw. Other than time required to use the program, we do not anticipate any common reasons for withdrawal that we will plan for in advance.

In rare cases, a Principle Investigator may decide to prematurely discontinue a participant's involvement in the study for any of the following reasons:

- a) Safety,
- b) Participant non-compliance,
- c) A change in circumstance that would prevent completion of protocol-required assessments,
- d) Participant relocation to an area that, due to great distance, would prohibit a participant from receiving follow-up at the study site,
- e) Participant displays inappropriate behavior toward study staff members or other participants,
- f) Participant is hospitalized for psychiatric reasons;
- g) Loss of funding, or;
- h) A clinical determination, by the Principal Investigator, that continuation in the study is not in the participant's best interests.

Across all reasons for withdrawal, we will ensure an orderly end to the participant's involvement in the study by arranging for the Site Study Coordinator or WASABI Clinician to recover the mobile device (if it has been issued to the participant), conducting an informational interview with the participant to understand the reasons for study withdrawal and identify any issues with study conduct or adverse events that are relevant, and arrange study compensation for sessions that the participant completed.

Modifications to the Protocol

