Statistical Analysis Plan

WASABI: Wiring Adolescents with Social Anxiety Via Behavioral Interventions

Protocol Number: PSC-1016-19

NCT03990870

Document Date: July 8, 2019

(1) ANALYSIS POPULATIONS

There are three *a priori* defined analysis populations, including a primary analysis population (i), a secondary analysis population designed to compare effect sizes in populations with no missing data (ii) and a population who completed all training visits (iii)

- i. *Intent to Treat (ITT) population:* This is the *a priori* primary analysis population, defined as including all randomized participants who attended at least one group video call.
- ii. *Intent to Treat (ITT) Fully-Evaluable (FE) population:* This is a secondary analysis population, defined as including all members of the ITT population that complete a post-intervention visit. Note that a participant may complete a specific visit but have missing data for a test in which case the participant is in the overall FE population but does not contribute data to the FE population for that visit, e.g., the number of evaluable cases for a specific test on a specific visit may be smaller than the FE population for that visit because of missing data.
- iii. *Intent to Treat (ITT) Completers (C) population:* This is a secondary analysis population, defined as including all members of the ITT-FE population who complete all intervention sessions. Note that the C populations are strict subsets of the FE populations; a person who completes the target number of videocalls but does not complete the evaluation visit is not a member of the C population.

(2) STATISTICAL PLAN

Feasibility

The Phase I data analysis plan *a priori* defines a primary intent-to-treat (ITT) population, a set of secondary evaluation populations, a set of primary outcome measures, a set of secondary outcome measures, a set of potential mediators/moderators, a single primary evaluation time point, a criterion for statistical significance, and a statistical analysis methodology for secondary outcomes.

- The primary ITT population is defined as all participants who attend one dCBGT video call. Note that this includes all randomized participants except those who drop/withdraw post-randomization and pre-training.

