- As the main goal of this Phase I trial is to evaluate the feasibility, acceptability and usability of the WASABI app. To this purpose, we will conduct an analysis of the following primary outcome measures in participants randomized to the WASABI+dCBGT arm:
 1. Assessment adherence (percentage of assessment sessions attended). Efforts will be made to assess all participants who have completed the minimum required intervention activities (attended at least 2 group calls, completed EMAs at least five times). *Based on our previous studies (CLIMB and MOODIFY) and pilot, we expect successful data collection of baseline and post-intervention outcome measures for ≥90% of participants.*
 2. Engagement with the digitally delivered Cognitive Behavioral Group Therapy (dCBGT) and with group Instant Messaging (IM): number of group sessions attended, number of messages sent per week on the group chat. *Based on our previous studies (CLIMB), we hypothesize that participants randomized to WASABI+ dCBGT will participate in 80% of the dCBGT sessions, and send at least 8 messages/week in the group chat.*
 3. EMA completion rate. *Based on our previous studies and pilot, we hypothesized that participants randomized to WASABI+ dCBGT would respond to 70% of the EMA prompts.*
 4. SPAI-B completion rate. *Based on our previous studies and pilot, we hypothesized that participants randomized to WASABI+ dCBGT would complete the weekly SPAI-B questionnaire 70% of the time.*

5. Overall program completion rate. *Based on findings from our previous findings (CLIMB) and from the pilot in anxious youth, we hypothesized full program completion in $\geq 79\%$ (≥ 8 of 12) study participants in the treatment arm.*

6. Usability ratings were obtained from all study participants post-intervention via a 7-point Likert-scale exit survey. This is a brief and embedded post-study questionnaire on program satisfaction, clarity, enjoyment, perceived benefits, and ease of fit into schedule. Participants rate each sentence on the following 7-point Likert scale: 1 = Completely Agree; 2 = Mostly Agree; 3 = Somewhat Agree; 4 = Undecided; 5 = Somewhat Disagree; 6 = Mostly Disagree; 7 = Completely Disagree. Clinical trials run by Posit Science software using this survey have shown high internal consistency with a Chronbach's alpha of .917. *Based on our previous findings, we hypothesize exit survey ratings of at least $\geq 4.5 \pm 1.5$ on the 7-point Likert scale items.*

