For feasibility, we relied on descriptive statistics. For preliminary efficacy, in smaller sample sizes like ours, there is a greater likelihood that there will be larger differences at baseline between groups simply due to sampling error. Groups were compared on all baseline measures using Mann-Whitney U tests (for ordinal and continuous variables) or Pearson chi-square/Fisher's exact test (for categorical variables). To test whether groups differed in change over time, data were analyzed via linear mixed-effects models. Mixed-effects models are ideal for the analysis of longitudinal data, due to the fact that it tolerates missing observations—assuming that it is missing at random (MAR). First, simple growth models (change from baseline to post) were conducted to examine change over time (for all participants). Because complete case analyses have been shown to provide biased estimates in the presence of missing data (Enders, 2010), data were then modeled using the intent-to-treat (ITT) framework, in which all randomized subjects are included in the analysis, and missing data were handled via Full Information Maximum Likelihood (FIML). This method for handling missing data is considered a gold standard approach, as it gives relatively unbiased estimates (Enders, 2010), and is the standard for the analysis of randomized trials. For all models, fixed effects of time, group, and group x time interaction were included; a random intercept of subject was used. Kenward-Roger degrees of freedom were used due to the small sample size; statistical significance was evaluated at a two-sided alpha of $p = 0.05$; however, null hypothesis testing was de-emphasized given the small sample size of the control group ($n = 8$). We emphasize the effect size (Cohen's d) instead. Although various estimates of effect size exist for LMM, we chose a simplified version, defined as:

$$\frac{(\Delta_{(dCBT+WASABI)} - \Delta_{(dCBT)})}{\sigma_{pre}}$$

Where Δ refers to slope (i.e., change from baseline to post-intervention) and σ_{pre} refers to the pooled baseline standard deviation. Thus, values of d refer to change in standard deviation units from baseline.

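### Minor: the post-intervention visit (V3) is conditional on an undefined session minimum for participants who stop early, and missing V3 scores are then analysed under MAR alone, with no sensitivity range

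*SAP*

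**What the plan says.** **Analysis.** SAP section (2) uses a two-visit linear mixed model with time, group, their interaction and a random subject intercept. Missing data are handled by full-information maximum likelihood, justified because "it tolerates missing observations—assuming that it is missing at random (MAR"). It puts the weight on a between-arm d, the difference in change divided by the pooled baseline SD.

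**Who is asked for V3.**
- Protocol, *Withdrawal from the Protocol*: someone wishing to leave because of the time required may stop the intervention and still attend V3, "given they have met the minimum sessions required to complete the post-assessment visits".
- Protocol, *Description of Protocol Devices*: those who attend few sessions have V3 after 12 weeks, "given that they have met the minimum number of sessions required to complete this visit". The paragraph on ceasing program use adds a similar condition.
- Neither section defines the minimum. SAP section (2), primary outcome 1, directs assessment efforts to those "who have completed the minimum required intervention activities (attended at least 2 group calls, completed EMAs at least five times"). Protocol *Data Analysis* gives the same figures.

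**Exceptions.** Participants meeting the C-SSRS criteria are asked for a final assessment if appropriate (Exclusion criteria, item 8; *Screening Procedures*). Participants who cannot be reached and hold a loaned device are invited back by letter (*Study Procedures/Research*, item 7). No session minimum is attached to either.

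**Withdrawal for worsening.** The consent section says: "If a participant is hospitalized for psychiatric reasons during the study, they will be withdrawn from study activities". The withdrawal section makes the same event a discretionary reason and calls investigator discontinuations rare. The adverse-event section also lets the investigator remove a participant when continuing is no longer in that participant's interest.

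**Populations.** ITT is "all randomized participants who attended at least one group video call". The fully evaluable set is defined as "including all members of the ITT population that complete a post-intervention visit", and Completers are a subset of it.

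**The concern.** The primary population needs one call, while the only stated threshold for pursuing V3 is two calls plus five EMA sessions. If that is the minimum the Protocol means, the plan itself leaves some primary-population outcomes uncollected. Controls have no EMAs during the intervention, so the EMA half of the threshold can bind only in WASABI.

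With two visits and a random intercept, a participant without V3 contributes only a baseline. The model in effect credits that person with roughly the average change seen in their own arm. That is reasonable if they left for unrelated reasons, and too favourable if they left because they were deteriorating.

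The fully evaluable and Completers sets cannot show this, because both require an observed V3. The between-arm d is the quantity the SAP emphasises, and Protocol *Data Analysis* says these measures will help power Phase II.

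**Working it through.** **What the plan allows for.** No effect of missing data is stated, so there is no figure of that kind to reproduce. Two planning figures bear on how many cases to expect.
- SAP primary outcome 1: "we expect successful data collection of baseline and post-intervention outcome measures for ≥90% of participants", listed among the WASABI-arm outcomes. With 12 in the arm, 11/12 = 92% meets the target and 10/12 = 83% does not, so one missing V3 fits the plan. Protocol *Data Analysis* applies the measure to those who met the activity minimum, so ITT members below it come on top.
- Protocol *General Study Design*: about 32 consented for 24 completers. 1 − 24/32 = 25% is an upper limit for loss after randomisation, because it includes screen failures.

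**Inputs.**
- From the documents: 12 planned per arm, and control n = 8 in the SAP's closing paragraph.
- Assumed: 12 in WASABI against those 8 controls; pre/post correlation ρ = 0.5; other participants improve by 0.5 to 1.0 baseline SD; the missing post score is truly between the participant's own baseline (δ = 0) and 1.0 SD worse (δ = 1.0); the missing participant's baseline is at the arm mean.

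**Shift in d.** For k missing cases in an arm of n, shift = (k/n) × (δ + improvement of the others). The bracket runs from 0 + 0.5 = 0.5 SD to 1.0 + 1.0 = 2.0 SD.

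| Offset (SD) | One WASABI case, offset/12 | One control case, offset/8 |
|---|---|---|
| 0.5 | 0.042 | 0.063 |
| 1.0 | 0.083 | 0.125 |
| 1.5 | 0.125 | 0.188 |
| 2.0 | 0.167 | 0.250 |

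A WASABI case moves d in WASABI's favour and a control case moves it in control's favour. Simulated likelihood fits of the two-visit random-intercept model (800 runs per setting) gave 0.043 to 0.173 and 0.066 to 0.268, in line with the formula.

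**One case in each arm.** 0.063 − 0.042 = 0.02 up to 0.250 − 0.167 = 0.08, in control's favour. At the planned 12 v 12 the two cancel and d is unchanged, although within-arm change is still overstated in both arms.

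**Baseline severity.** Each SD by which the missing participant is more severe at baseline than the arm mean adds (1 − 0.5)/12 = 0.04 for WASABI or (1 − 0.5)/8 = 0.06 for control. Each SD less severe subtracts the same.

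**Against sampling error.** SE(d) = √[2(1 − ρ)(1/12 + 1/8)] = √0.208 = 0.46 at ρ = 0.5, 0.54 at ρ = 0.3 and 0.35 at ρ = 0.7. The largest one-case shifts are 0.167/0.456 = 0.37 SE and 0.250/0.456 = 0.55 SE.

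**Other arm size.** The WASABI n is not stated. If it were 16, one WASABI case would shift d by 0.5/16 = 0.03 to 2.0/16 = 0.125.

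**The case against.** The best defence has four parts.

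1. **The condition may be narrower than it looks.** The general study design and the visit list describe V3 with no minimum. The withdrawal section's conditional offer covers only people leaving for lack of time. The two-call, five-EMA figure belongs to an adherence outcome and is never tied to the other sections. This stands in part. A reader might infer that every early leaver other than C-SSRS cases is shut out of V3, but the device-return letter rules that out. Equating the two minima is an inference. The *Description of Protocol Devices* section still attaches a condition for those who attend few sessions or stop program use.

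2. **Absence by rule depends on recorded attendance, and the plan uses program use.** Protocol *Data Analysis* makes total program use time a covariate if the arms differ at p < 0.1, and correlates outcome change with engagement. This is partial cover. The covariate enters only if the test is met and does not record why someone left. The correlation needs an observed V3.

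3. **The effect is swamped by sampling error.** This is true for any one-case shift. A wide interval does not reveal bias, however, and the point estimate is what the SAP emphasises.

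4. **Withdrawal reasons are already collected** at an exit interview. This is correct. The gap is in planned reporting, which makes the remedy cheap.

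**Conclusion.** The point holds as a minor one. The plan can leave ITT members without V3 through its own session condition or through withdrawal for worsening. It relies on MAR alone for them, and neither secondary population tests that assumption.

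The size is modest: 0.04 to 0.17 for one WASABI case and 0.06 to 0.25 for one control case, against an SE of about 0.46. Apart from the control n of 8, these figures rest on assumed inputs (WASABI n, correlation, improvement and severity of the missing score). The top of each range combines good improvement in the others with marked worsening in the missing participant.

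Two stronger readings are tempting and not supported.
- **That the estimate is biased towards WASABI.** The EMA half of the minimum could bind only there, but the sign depends on which arm loses cases, and nothing in the documents says which will.
- **That the main analysis is wrong.** The outcomes affected are secondary, the Protocol disclaims power for the between-arm effect, and the number of relevant cases may be zero.

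**What to change.** Keep the mixed model and make two changes.

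1. **If data collection is still open**, remove the session condition in *Withdrawal from the Protocol* and *Description of Protocol Devices*. Ask for V3 from all randomised participants where it is safe and they are willing, whatever number of sessions they attended.
2. **If any V3 is missing**, add to SAP section (2) a delta-adjusted range for d on each secondary outcome. Set the missing post score to the participant's baseline, then 0.5 and 1.0 baseline SD in the worse direction, by the same rule in both arms. Label it as sensitivity only, without p-values. Report beside it a table of withdrawals by arm and reason.

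The last weekly SPAI-B should not stand in for V3. Only WASABI participants complete it weekly, so this would treat the arms differently.

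**Cost.** Each extra visit takes about 2 hours and a $75 payment. The rest is a short Protocol edit, one SAP paragraph, one table from data already collected and a few model runs. The SAP's closing paragraph is in the past tense, so only item 2 may still be possible.

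**Downsides.** The fixed values are crude and carry no imputation uncertainty. A withdrawn participant may still decline V3. The reported d may look slightly less favourable.

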Once three participants are deemed eligible and enrolled in the pilot trial, they will be scheduled for three focus group sessions that could occur in-person or remotely, to be completed over the course of approximately 2-weeks. Each session will last approximately 1 hour and will be facilitated by the study clinician(s). After feedback from the focus group sessions is implemented into the app and dashboard design, the three adolescents will be granted access to the WASABI app and engage in a 2-week trial period, during which the predictive ability of the algorithm will be validated by the WASABI clinician, who will verify via 1:1 remote videocalls the actual presence of clinically-significant social anxiety whenever the WASABI clinician receives an alert. Additionally, this trial period will ensure that WASABI EMA data are timely evaluated by the clinician on the dashboard and meaningfully orient the delivery of individualized IM and weekly dCBGT content. At the end of the 2-week trial period of WASABI, participants will be asked to rate their enjoyment, ease of use, product quality, and perceived usefulness in a 1:1 user interview. Finally, we will submit these data from the trial period to our consultant to confirm that WASABI is suitable for the feasibility trial.

General Study Design

We will employ a standard prospective, parallel arm, double-blind, randomized, controlled clinical trial to assess the safety and efficacy of WASABI in adolescents with Social Anxiety (SA), and evaluate its potential in augmenting the efficacy of dCBGT in improving social

anxiety, social skills and social functioning. We will randomize adolescents with SA (ages 14-18) to receive either 12 weeks of dCBGT+WASABI or dCBGT only.

Approximately 32 participants will be consented to ensure the successful completion of 24 participants (12 participants per treatment arm). A diagnostic interview will be performed to determine eligibility. Following inclusion and enrollment, participants will complete a set of assessments prior to the intervention to establish their baseline performance. Participants will then be randomized to dCBGT+WASABI or dCBGT only and spend up to 12 weeks engaged in their assigned intervention.

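### The SAP's group-by-time estimate is an unadjusted change-score contrast; a common-baseline model would remove most of the chance-imbalance shift and modestly cut the standard error

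*SAP*

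**What the plan says.** The last paragraph of SAP (2) Statistical Plan sets out the efficacy model. Its terms are "fixed effects of time, group, and group x time interaction were included", and "a random intercept of subject was used". The data enter at two times: "simple growth models (change from baseline to post) were conducted to examine change over time". The reported effect size d is the between-arm difference in Δ, divided by the pooled baseline SD, where Δ "refers to slope (i.e., change from baseline to post-intervention". No baseline covariate is named, and nothing constrains the arms to share a baseline mean. Missing values are handled by full-information maximum likelihood, with Kenward-Roger degrees of freedom.

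The same paragraph says that in small samples "there is a greater likelihood that there will be larger differences at baseline between groups simply due to sampling error". It then compares the arms at baseline with rank and chi-square or Fisher tests, and states no consequence for the model. It puts d ahead of p-values: "null hypothesis testing was de-emphasized given the small sample size of the control group ($n = 8".

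The Protocol's Data Analysis section goes further. Baseline factors that differ at p<0.1, outcome scores included, become covariates in the mixed model. Its Screening Procedures section also promises medication covariates. Neither commitment appears in the SAP model.

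On numbers, the SAP's completion target refers to "≥ 8 of 12) study participants in the treatment arm", and the Protocol's General Study Design aims "to ensure the successful completion of 24 participants (12 participants per treatment arm".

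**The concern.** A mixed model can look as if it deals with baseline differences. This one does not. Group has its own free effect at baseline, so the interaction subtracts the whole baseline difference, as if post scores tracked baseline scores one for one. With a pre-post correlation below 1 that over-corrects. On a symptom scale, the arm that happens to start more severe will tend to show the larger improvement, through regression to the mean.

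The SAP makes d the headline efficacy quantity. The Protocol's Sample Size Justification says the pilot data, between-arm differences among them, will be used to power the Phase II trial. Required sample size scales with 1/d², so avoidable error in d carries forward.

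**Working it through.** **Inputs.** Control n = 8 (SAP efficacy paragraph). Treatment n = 12 (the SAP completion target's denominator and the Protocol's planned arm size). N = 20. Assumptions: equal SDs before and after treatment, and only two time points in the model. The documents give no rho, so a range is shown. They also give no power figure, SD or expected effect, so there is no figure of the plan's own to reproduce.

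**1. What the interaction estimates.** The SAP model was fitted to two simulated complete 12 v 8 data sets. The interaction equalled the difference in mean change both times: −0.48989 v −0.48989, and 0.06264 v 0.06264. With three post values missing it no longer equals the complete-case change difference (−0.321 v −0.257; 0.153 v 0.054), but the baseline means are still unconstrained.

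**2. Whether the Protocol's rule would repair it.** In a further simulated data set the interaction was 0.2074. Adding the baseline score as a main effect left it at 0.2074. Adding baseline and baseline × time gave 0.5418, the ANCOVA value. The trigger is also insensitive. Taking a t test as a stand-in for the rank test, p<0.1 on 18 df needs an observed difference of about 1.734 × 0.456 = 0.79 SD.

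**3. Size of chance imbalance, in baseline SD units.** SD of the baseline mean difference = √(1/12 + 1/8) = 0.456. Median absolute value = 0.6745 × 0.456 = 0.31. It exceeds 0.5 in 27% of randomizations. At the planned 12 v 12 the SD would be √(2/12) = 0.408.

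**4. Shift in d, given the imbalance.** The magnitude is (1 − rho) × imbalance. In simulation the change-score estimate regressed on the imbalance with slopes −0.50 (rho 0.5), −0.31 (0.7) and −0.20 (0.8); for ANCOVA the slope was about 0.

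| rho | shift at one-SD imbalance (0.456) | shift at median imbalance (0.31) |
|---|---|---|
| 0.5 | 0.23 | 0.15 |
| 0.7 | 0.14 | 0.09 |
| 0.8 | 0.09 | 0.06 |

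**5. Precision.** Change score: variance = 2(1 − rho)(1/12 + 1/8). ANCOVA: variance = (1 − rho²)(1/12 + 1/8) × (N − 3)/(N − 4), where the last factor, 17/16, is the small-sample cost of estimating the slope. The ratio is therefore (1 + rho)/2 × 17/16. The common-baseline ratios come from 40,000 simulated trials per rho. The fall in SE is 1 − √ratio.

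| rho | ANCOVA variance ratio | SE falls by | common-baseline variance ratio | SE falls by |
|---|---|---|---|---|
| 0.5 | 0.80 | 11% | 0.78 | 12% |
| 0.7 | 0.90 | 5% | 0.87 | 7% |
| 0.8 | 0.96 | 2% | 0.92 | 4% |

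ANCOVA breaks even where (1 + rho)/2 = 16/17, at rho of about 0.88. The common-baseline ratio was below 1 at every rho simulated (0.96 at rho 0.9).

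**6. What remains.** The 95% interval half-width for d goes from 0.96 to 0.86 with ANCOVA at rho 0.5, and from 0.74 to 0.71 at rho 0.7.

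**The case against.** A group-by-time mixed model is valid and common. The efficacy measures are secondary, feasibility is descriptive, testing is de-emphasised, and the Protocol concedes inadequate power. The interval for d stays too wide to fix a Phase II sample size with or without adjustment. The Phase II link is itself ambiguous: the Protocol's Data Analysis section mentions powering straight after within-group effect sizes, which between-arm adjustment would not change. All of this stands, and it limits the importance of the point.

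Three stronger readings are tempting, and none is supported:

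- **That the plan yields a biased treatment effect.** Over all randomizations the change-score contrast is unbiased. The shift is conditional on the imbalance that occurred.
- **That the sponsor planned nothing for imbalance.** The Protocol has its p<0.1 rule. The problem is that the SAP drops it, that it rests on an insensitive pretest, and that as a main effect it does not alter the interaction.
- **That the precision gain is the textbook (1 + rho)/2.** That is a large-sample ratio, implying SE reductions of 13% at rho 0.5 and 8% at rho 0.7. At N = 20 both remedies give less.

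Some premises are also soft. The 12 v 8 split joins a completion target to a control count. Complete baseline data cannot be taken for granted: the SAP expects baseline and post data for at least 90%, and the Protocol lets participants skip assessments. Weekly SPAI-B scores exist in the WASABI arm only, and the SAP does not say whether they enter the model.

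**Conclusion.** The point holds as a modest, nearly free improvement to the quantity that the SAP chooses to emphasise. With complete two-time-point data the planned estimate makes no baseline adjustment, and neither the SAP's baseline tests nor the Protocol's covariate rule as worded supplies one. A typical (median) imbalance moves d by roughly 0.1 to 0.15, and a one-SD imbalance by 0.14 to 0.23, for rho between 0.7 and 0.5. The possible SE reduction is 4% to 12% for rho from 0.8 down to 0.5, and smaller at higher rho. These sizes rest on 12 v 8, equal SDs and an assumed rho. The change is worth making, but it does not make d precise and the feasibility conclusions do not depend on it.

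**What to change.** - **Main estimate.** For each efficacy measure, fit the same mixed model with one common baseline mean (time and group × time, no group effect at baseline). Keep maximum-likelihood handling of missing data, Kenward-Roger degrees of freedom and scaling by the pooled baseline SD. This is preferable to ANCOVA here, which gains less at N = 20 and nothing above rho of about 0.88.
- **Sensitivity analysis.** Report the unadjusted difference in mean change alongside.
- **Reconcile the documents.** Replace the Protocol's p<0.1 rule for baseline outcome scores with this pre-specified model, and say in the SAP what becomes of the other promised covariates. State whether weekly SPAI-B scores enter the model.
- **Timing.** The SAP paragraph is in the past tense and states the control group size. If outcomes have already been seen, date the change, label it post hoc and show both estimates.

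The cost is about one line of SAP text and code. No new data are needed: Protocol Appendix I schedules LSAS-CA, SPAI, MASC-2, ASSES and SSQ at both V1 and V3, and the embedded SPAI-B is taken before and after treatment in both arms.
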